4.6.5. Transplant-Related Mortality

Transplant-related mortality will be determined by the Investigator and summarized for the following intervals: from the Informed Consent through 100 days post-drug product infusion, and from the Informed Consent through 365 days post-drug product infusion.

4.6.6. Overall Survival

Overall Survival (OS) is defined as time from date of drug product infusion (Day 1) to date of death. Overall survival will be censored at the date of last follow-up if subject is alive. If there is any death due to any reason occurring during the study, OS rate at 12 months and 24 months by Kaplan-Meier method will be reported.

4.6.7. Persistent Oligoclonality and Integration Site Analysis (ISA)

Persistent oligoclonality is defined as RelFreq of $\geq 10\%$ for the same IS at two consecutive timepoints or RelFreq $\geq 5\%$ for the same two or more IS at two consecutive timepoints.

Persistent oligoclonality at any time is defined as a subject meeting the criteria of persistent oligoclonality at any time during the study, including cases when the criteria are no longer met in later follow-up assessments.

Current persistent oligoclonality is defined as a subject meeting the criteria of persistent oligoclonality at the last two assessments as of the data cut-off. It is a subset of persistent oligoclonality at any time.

Current oligoclonality is defined as RelFreq $\geq 10\%$ for at least 1 IS or RelFreq $\geq 5\%$ for two or more IS at the last assessment as of the data cut-off.

ISA results from bone marrow may also be considered in the above algorithm. If an IS is measured from multiple blood or tissue samples (i.e., concurrent peripheral blood and bone marrow samples), the higher IS RelFreq will be used. Samples taken more than 30 days apart

will be considered distinct consecutive timepoints. Additionally, IS-VCN results collected from IS-specific qPCR per historical protocols will not be considered in the above algorithm.

The number and percentage of subjects meeting persistent oligoclonality at any time, current persistent oligoclonality, and current oligoclonality will be summarized.

IS RelFreq overtime will be plotted for subjects with IS meeting oligoclonality (persistent oligoclonality at any time, current persistent oligoclonality and/or current oligoclonality will be indicated).

Top 10 RelFreq results for each subject overtime will be presented in listings.

In addition, the total number of unique mappable IS at each assessment, as well as the highest RelFreq and highest total number of unique mappable IS within subjects across all assessment, will be summarized. Additional analysis may be performed as appropriate.

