2.2.3. Safety Endpoints

Safety will be evaluated by the following:

- Safety and tolerability of plerixafor for mobilization
- Success and kinetics of HSC engraftment
- Transplant-related mortality through 100 days post-drug product infusion and through 365 days post-drug product infusion
- Detection of vector-derived replication competent lentivirus (RCL) in any subject
- The number of subjects with insertional oncogenesis (myelodysplasia, leukemia, lymphoma, etc.)
- The number of subjects with persistent oligoclonality
- Frequency and severity of AEs/SAEs
- Laboratory parameters over time, including the following immunology tests:
Screening for irregular antibodies, lymphocyte subpopulation evaluation (CD3, CD4, CD8, CD19, CD16/CD56)
- Incidence of acute and/or chronic graft-versus-host disease (GVHD)
- Other safety labs over time: chemistries, LFTs (AST, ALT, ALP, GGT, bilirubin [total and direct]), hematology, coagulation parameters
- Hormonal testing over time: estradiol (females only); total testosterone (males only) TSH, free T3, free T4, cortisol, ACTH, FSH, LH (all subjects)
- Change from baseline in methemoglobin concentration at Month 12 and Month 24
- Number of subjects with presence of a chromosomal abnormality or genetic mutation associated with hematologic malignancies over time

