6.2.28. Assessment of Oligoclonality by Integration Site Analysis

[figure not shown]
Integration site analysis (ISA) will be performed to determine the insertion site (IS) profile of subjects over time, as indicated in the SOE. Figure 4 shows the algorithm that determines the

frequency of monitoring by ISA to assess oligoclonality, in accordance with FDA Guidance ([FDA 2020](#)). While oligoclonality itself, or even monoclonality, will not a priori result in a malignancy, changes in IS relative frequency may be associated with an increase in the risk of a malignancy. Therefore ISA monitoring is performed every 6 months for the first 5 years after drug product administration, and annually thereafter. This is coupled with monitoring for hematological abnormalities via complete blood count (CBC) with differential every 6 months through 15 years after drug product administration (see [Section 6.2.33](#) for information on long-term follow-up).

ISA monitoring may be repeated more frequently if there is an indication of oligoclonality. As shown in [Figure 4](#), if an IS is detected at $\geq 10\%$ relative frequency (RelFreq) for 1 IS, or $\geq 5\%$ RelFreq for ≥ 2 IS each, ISA will be repeated within 3 months of receipt of this result. If the result is confirmed, a report of persistent oligoclonality will be submitted to the relevant Health Authorities within 30 days. This repeated observation will also trigger enhanced monitoring for hematological abnormalities, increasing the frequency of CBC with differential to every 3 months along with ISA and VCN every 6 months until the criteria for oligoclonality is no longer met.

Based on clinical and ISA findings, additional monitoring for malignancy may be instituted by the treating physician/Principal Investigator or Sponsor. See the following section for recommended clinical work-up for malignancy.

Figure 4: Algorithm for Frequency of ISA Monitoring

Abbrev.: IS, insertion site(s); ISA, integration site analysis; RelFreq, relative frequency

^a ISA is assessed per the schedule of events; CBC with differential and VCN are to be carried out whenever ISA is performed ([Table 4](#)).

^b If ISA is assessed concurrently from PB and BM, the assessment with higher RelFreq values should be used.

^c Samples obtained one month or more apart can be considered consecutive measurements.

[figure not shown]
^d Persistent oligoclonality will be reported to the relevant Health Authorities within 30 days.

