4.6.2	Engraftment	Added a supplementary analysis for time to PE. This is to extend the time to PE for subjects who took eltrombopag before achieving PE to align with the label.
4.6.3	Laboratory Data	Added hematology RDW test. Added the analysis of cytopenia.
4.6.7	Persistent Oligoclonality and Integration Site Analysis (ISA)	Updated the algorithm used for ISA to align with Protocol Version 13.0.
6.1	Imputation Rules for Missing Data	Updated the imputation rule for AE end date by replacing data cut-off date with last follow-up date. Updated the imputation rule for missing adjudicated VOE end date.
6.2	Analysis Visit Windows	Added analysis visit window for RDW.
6.7	Search Strategy for Events of Interest	Added thromboembolic events

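### SAP 4.6.7 does not count as persistent a subject whose second oligoclonal result rests only on one of the first result's clones having grown to 10% or more

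*SAP*

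**What the plan says.** The endpoint appears among the safety endpoints in Protocol 2.2.3: "The number of subjects with persistent oligoclonality".

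SAP 4.6.7 gives persistence two limbs, each carrying its own repeat condition. The first is RelFreq of at least 10% "for the same IS at two consecutive timepoints or RelFreq" of at least 5% "for the same two or more IS at two consecutive timepoints", which is the second limb. Samples more than 30 days apart "will be considered distinct consecutive timepoints". *Current persistent oligoclonality* applies the same rule to the last two assessments.

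At a single assessment the criterion is looser. *Current oligoclonality* is met by at least 10% for one IS, or at least 5% "for two or more IS at the last assessment as of the data cut-off". Either limb is enough, and identity with an earlier IS is not required.

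Protocol 6.2.28 triggers a repeat ISA on either limb, within 3 months of receiving the result. It then says: "If the result is confirmed, a report of persistent oligoclonality will be submitted to the relevant Health Authorities within 30 days". Enhanced monitoring continues "until the criteria for oligoclonality is no longer met". SAP 5.2 records the change to this section as: "Updated the algorithm used for ISA to align with Protocol Version 13.0".

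**The concern.** Because the repeat condition attaches to each limb separately, a subject can be oligoclonal at two consecutive assessments, with the same IS contributing to both, and satisfy neither limb twice. This happens when the first assessment qualifies through two or more IS between 5% and 10%, one of them then passes 10%, and none of the others is still at 5% or more. A subject whose two clones do not change is counted; the same subject with one clone expanding may not be.

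RelFreq values are shares of a total, so growth of one clone lowers the share of the rest. The switch of limb can therefore result from the expansion itself. At stake is a named safety count for an integrating vector, which can fall when a clone grows.

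**Working it through.** **Inputs.** The persistence and single-assessment rules and the 30-day spacing are from SAP 4.6.7. ISA is scheduled at Months 6, 12, 18 and 24 (Protocol Table 4), with the triggered repeat in Protocol 6.2.28 and a typical turnaround of about 10 weeks (Protocol Figure 5, note b). Numbers infused are 7, 1, 1 and 36 in Groups A, B1, B2 and C (SAP Table 1). The documents give no RelFreq data and no figure of their own to reproduce, so all trajectories below are illustrative assumptions.

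**Step 1: apply the rule as written.** Every row meets the single-assessment criterion at both timepoints.

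| IS-A/IS-B, first then second (%) | Same IS ≥10% twice | Same two IS ≥5% twice | Persistent |
|---|---|---|---|
| 9/5.5 then 9/5.5 | no | yes | yes |
| 9/5.5 then 33.1/4.0 | no | no | **no** |
| 6/6 then 12/4 | no | no | **no** |
| 6/6 then 12/5.5 | no | yes | yes |
| 12/2 then 8/6 | no | no | **no** |

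The gap depends on the companion IS. Take whole-percentage values with both IS at 5–9% first, then IS-A at 10–30%. With IS-B at 0–4% second, all 5 × 5 × 21 × 5 = 2,625 combinations are missed. With IS-B at 5–9% second, none of 2,625 is missed. These counts describe the rule; they are not probabilities.

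**Step 2: can expansion alone cause the switch?** If IS-A expands k-fold and all other clones stay constant:

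A′ = 100·A·k / (A·k + 100 − A), B′ = 100·B / (A·k + 100 − A).

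For A = 9, B = 5.5, k = 5 the denominator is 45 + 91 = 136. So A′ = 4500/136 = 33.1% and B′ = 550/136 = 4.0%.

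For A = 9, B′ < 5% requires 9k + 91 > 20B, and A′ ≥ 10% requires k ≥ 910/810 = 1.12. The gap therefore opens as follows:

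| B at first assessment | k just above | A′ about |
|---|---|---|
| 5.0% | 1.12 | 10% |
| 5.5% | 19/9 = 2.11 | 17% |
| 6% | 29/9 = 3.22 | 24% |
| 7% | 49/9 = 5.44 | 35% |

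A companion near 5% is lost with little growth. One at 7% needs a large expansion.

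**Step 3: how long does the miss last?** If 6/6 then 12/4 is followed by 14/3, IS-A is at least 10% twice and the subject becomes persistent. The any-time count then keeps the subject. Scheduled visits are not the only opportunities. A Month 18 finding, with 10 weeks (2.3 months) to a result and up to 3 months to the repeat, gives a repeat by about 18 + 2.3 + 3 = 23.3 months. If that repeat is earlier, or the Month 24 visit falls late in its ±30-day window, the two samples can be more than 30 days apart. The miss lasts when no later in-study result has that IS at 10% or more, for example when the switch occurs at the last in-study ISA.

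The *current persistent* count is affected separately. With 6/6, 6/6, then 12/4 as the last assessment, the subject is persistent at any time through the first pair but not currently persistent, although the last assessment still meets the single-assessment criterion.

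**Step 4: size per subject.** 1/36 = 2.8 percentage points of Group C. Infused overall: 7 + 1 + 1 + 36 = 45, and 1/45 = 2.2 points.

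**The case against.** Requiring the same signal twice is a defensible meaning of persistence: an IS seen once at 10% or more has not yet persisted at that level. The rule is not slanted only against growth either, since a contracting pattern such as 12/2 then 8/6 is also left out. Both points stand, and they are reasons to report a mixed-limb pattern in its own row rather than merge it silently.

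Other planned outputs also limit the harm. SAP 4.6.7 lists each subject's ten highest RelFreq values over time, plots subjects meeting oligoclonality, summarises the highest RelFreq, and counts current oligoclonality. A 33% clone would be visible. No test, alpha or success criterion depends on the count, and monitoring and Health Authority reporting follow Protocol 6.2.28 rather than the SAP tabulation. That stands too, but none of it corrects the named count.

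A reader might infer more than the documents support:
- *Any expansion past 10% removes a subject.* It does not if a second IS from the first assessment stays at 5% or more (6/6 then 12/5.5).
- *Only three pairs of assessments exist, so a switch between Months 18 and 24 is never counted.* The triggered repeat ISA contradicts this.
- *The SAP contradicts the protocol.* This cannot be shown. The visible text of Protocol 6.2.28 states no same-limb or same-IS condition, but a confirmed result could naturally mean the same result again. The algorithm itself is in Figure 4, which was not available for this review.

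**Conclusion.** The point holds in a limited form. As written, SAP 4.6.7 omits a subject who is oligoclonal at two consecutive assessments when the second qualifies only because one of the first assessment's IS, previously below 10%, has reached 10% and no other IS from that assessment remains at 5% or more. Nothing else in the SAP covers a switch between limbs. The omission is often temporary, but becomes lasting if no further in-study result has that IS at 10% or more. It can also take a subject out of the current persistent count.

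The conclusion rests on the literal wording of the SAP. The trajectories only show that the gap is reachable, assuming other clones stay constant. Its frequency is unknown. Each affected subject moves the count by one (2.8 points in Group C, 2.2 overall). This is a low-cost improvement to a descriptive safety count; no inferential result is at risk.

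**What to change.** Add one sentence to SAP 4.6.7, applied to both the any-time and the current persistent counts: *A subject who meets the oligoclonality criterion at two consecutive timepoints without satisfying either same-limb rule is also counted as persistent if an IS with RelFreq ≥10% at the later timepoint was one of the two or more IS with RelFreq ≥5% that met the criterion at the earlier timepoint.*

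Report the present same-limb count and this mixed-limb count in separate rows. Reconcile the SAP definition with Protocol 6.2.28 and Figure 4, so that it is clear what a confirmed result means.

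The link to a specific earlier IS is deliberate. A looser rule asking only for one IS at 5% or more both times would count IS-A/IS-B at 5/5 followed by IS-A/IS-C at 5/5, where a single clone persists below the one-IS threshold. It would also count 12/2 then 8/6. The sentence above counts neither.

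The cost is one sentence, a small programming change and one extra table row. The reported count may be slightly higher.

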4.6.8. Replication Competent Lentivirus (RCL)

Blood will be tested for RCL at Month 3, 6, 12, and 24 Visits. If RCL screening tests are negative up to and including the Month 12 Visit, RCL screening will cease, and the Month 24 co-culture RCL sample only will be collected and archived. Results will be listed as detected, detected but not quantified, and not detected, and by co-culture assays (if applicable) detected or not detected, for each visit.

4.6.9. Dose-Limiting Toxicities (DLT) for Plerixafor for Subjects in Group B2

Three subjects in Group B2 including the two subjects re-assigned to Group C (PPI [REDACTED] and PPI [REDACTED] and PPI [REDACTED]) were required for evaluation of DLT at each dose of plerixafor. A listing for DLT for Plerixafor occurred in this study will be provided.

4.6.10. Chromosomal Abnormality or Genetic Mutation

Genetic testing by FISH (Fluorescence in situ hybridization), conventional cytogenetics (karyotyping) and NGS (next generation sequencing) will be summarized and presented in listings. The number of subjects with at least one abnormality will be summarized by test type (FISH, conventional cytogenetics, NGS, and all tests), sample type (blood, bone marrow, and both) and by time period (<Day 1, ≥Day 1 and overall). Listings will be presented separately for each type of genetic test. They will include date sample collected, sample type (bone marrow or blood), local or central laboratory assessment, and details about abnormalities.

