³⁰Baseline assessment should occur as close to Day -90 as possible, and where possible, must occur before start of pRBC transfusions. Subjects should complete PRO questionnaires at the beginning of the Visit (prior to undergoing any other procedures during the Visit.

Table 3: Schedule of Events: Conditioning and Drug Product Infusion

	Preconditioning Up to 7 days before busulfan	Conditioning Day -6 to -3 inclusive	Infusion Day 1	Day 2 until hospitalization discharge
Physical examination ^a	X	X	X ^b	X ^b
Performance status ^c	X			
Vital Signs ^d	X	X	X ^e	X ^f
Local lab: Blood for clinical laboratory tests				
Hematology ^g	X	X	X	X ^h
Serum Chemistry ⁱ	X	X	X	X
Coagulation Analysis ^j	X			
Iron Metabolism Studies ^k	X			
Haptoglobin	X			
Local lab: Blood for serology	X ^l			
Local lab: Blood for serum β -human chorionic gonadotropin for women of child-bearing potential (serum pregnancy test)	X			
Local lab: Blood for electrophoresis to assess globin fractions (i.e., %HbS, %HbA, %HbF)	X ^m			X ⁿ
Bone marrow aspiration ^o :				
Bone marrow smear ^p	X ^q			
Local lab: Bone marrow for conventional cytogenetics (karyotyping)	X ^q			
Central lab: Bone marrow for storage ^r	X ^q			
Central lab: Blood for next generation sequencing (NGS) mutational testing ^s	X ^q			
Central lab: Blood for storage ^r	X ^q			
Sperm / testicular tissue or oocyte banking, if requested	X			
Reconfirmation of suitability for transplant	X ^t			
Anti-seizure prophylaxis	X ^u	X ^u		
Busulfan chemotherapy (daily or q6h regimen, for 4 days)		X		
Local lab: Blood for busulfan pharmacokinetics ^v	X	X		
Infusion of bb1111			X	
Transfusion regimen	X ^w			

Table 3: Schedule of Events: Conditioning and Drug Product Infusion

	Preconditioning Up to 7 days before busulfan	Conditioning Day -6 to -3 inclusive	Infusion Day 1	Day 2 until hospitalization discharge
Vaso-occlusive event collection		Continuous from ICF signing		
Adverse event collection		Continuous from ICF signing		
Concomitant medication collection ^x		Continuous from ICF signing		

^a Any leg (skin) ulceration noted upon physical exam or as part of medical history must include severity classification.

^b To be performed on Day 1 before drug product infusion. A physical examination should be performed at least twice a week until discharge.

^c Karnofsky performance status (\geq 16 years of age) or a Lansky performance status ($<$ 16 years of age).

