Hematology ⁶	X	X	X	X	X	X	X	X	X	X	X
Serum Chemistry ⁷	X	X	X	X	X	X	X	X	X	X	X
Coagulation Analysis ⁸							X				X
Iron Metabolism Studies ⁹			X			X	X		X		X
Haptoglobin	X	X	X	X	X	X	X	X	X	X	X
Local lab: Hormonal testing ¹⁰							X				X
Local lab: Urinalysis ¹¹							X				X
Local lab: Blood for immunological studies ¹²			X		X	X	X				X
Screening for new irregular antibodies ¹³		X	X								
Local lab: Blood for BNP and Erythropoietin							X				X

Table 4: Schedule of Events: Follow-up

Procedures	Follow-Up: Day (D), Month (M) (Visit Window, days)										
	D30	D60	D90	D135	D180	D270	D360	D450	D540	D630	D720
	M1 (±7)	M2 (±7)	M3 (±7)	M4.5 (±14)	M6 (±14)	M9 (±14)	M12 (±30)	M15 (±30)	M18 (±30)	M21 (±30)	M24 (±30)
Central lab: Blood for globin and VCN ¹⁴	X	X	X	X	X	X	X	X	X	X	X
Central lab: Blood for RCL detection			X		X		X				X ¹⁵
Central lab: Blood for ISA ¹⁶					X		X		X		X
Central lab: Blood for NGS mutational testing ¹⁷							X				X
Central lab: Blood for storage ¹⁸	X	X		X		X		X		X	
Central lab: Blood for potential biomarker analysis (optional)							X				X
Specialty lab: Blood for methemoglobin assay							X				X
bluebird bio lab: Blood for CCI PD			X		X		X		X		X

Table 4: Schedule of Events: Follow-up

Procedures	Follow-Up: Day (D), Month (M) (Visit Window, days)										
	D30	D60	D90	D135	D180	D270	D360	D450	D540	D630	D720
	M1 (±7)	M2 (±7)	M3 (±7)	M4.5 (±14)	M6 (±14)	M9 (±14)	M12 (±30)	M15 (±30)	M18 (±30)	M21 (±30)	M24 (±30)
Bone marrow aspiration ¹⁹ :											
Bone marrow smear ²⁰							X				X
Local lab: Bone marrow for conventional cytogenetics (karyotyping) ²¹ :							X				X
Central lab: Bone marrow for NGS ¹⁷ , ISA ¹⁶ , storage ²² , and CCI PD							X				X
Imaging studies:											
Cerebral MRA/MRI ²³ , and, if ≤ 16 years of age, TCD							X				X
Echocardiogram (including LVEF and TRJV)											X
Cardiac MRI ²⁴											X
Liver MRI											X
Bone mineral density evaluation											X
Pulmonary function test ²⁵							X				X
6-minute walk test							X				X

Table 4: Schedule of Events: Follow-up

Procedures	Follow-Up: Day (D), Month (M) (Visit Window, days)										
	D30	D60	D90	D135	D180	D270	D360	D450	D540	D630	D720
	M1 (±7)	M2 (±7)	M3 (±7)	M4.5 (±14)	M6 (±14)	M9 (±14)	M12 (±30)	M15 (±30)	M18 (±30)	M21 (±30)	M24 (±30)
Quality of life tests: ²⁶ EQ-5D-3L/Proxy Version 1, EQ-5D-Y /Proxy Version 1, PROMIS-57 Version 2.1, PROMIS Pediatric Profile/Parent Proxy Profile 49 Version 2.0			X		X		X		X		X

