6.2.18. Conventional Cytogenetics (Karyotyping) and NGS Mutational Testing

Bone marrow aspirate (see [Section 6.2.17](#)) and blood will be collected according to the SOE for assessment of chromosomal abnormalities or genetic mutations, particularly those associated with myelodysplastic syndrome (MDS) or acute myeloid leukemia (AML), by conventional cytogenetics (karyotyping) and NGS mutational testing.

If available, bone marrow and blood samples collected per SOE may be used for retrospective genetic testing.

Results from conventional cytogenetics (karyotyping) from the bone marrow prior to conditioning will be used to assess suitability for transplant (see [Section 6.2.11](#)).

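### The genetic-abnormality safety table counts any abnormality before and after infusion, not the malignancy-associated ones the endpoint names, and can miss a new finding in a subject already positive

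*SAP*

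**What the plan says.** Protocol 2.2.3 lists among the safety endpoints: "Number of subjects with presence of a chromosomal abnormality or genetic mutation associated with hematologic malignancies over time". SAP 1.2.6.6 repeats it, and SAP 5.1 declares no change from the protocol's analyses.

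SAP 4.6.10 gives the analysis: "The number of subjects with at least one abnormality will be summarized by test type" (FISH, karyotyping, NGS, all tests), "sample type (blood, bone marrow, and both"), and "by time period (<Day 1, ≥Day 1 and overall"). Separate listings per test give the sample date, the sample type, "local or central laboratory assessment, and details about abnormalities".

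The specimens come from the protocol's schedule of events (6.1):

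- **Before conditioning (Table 3):** "Central lab: Blood for next generation sequencing (NGS) mutational testing", plus marrow for smear, karyotyping and storage. No marrow NGS is scheduled.
- **Follow-up (Table 4):** blood NGS, "Central lab: Bone marrow for NGS" and marrow karyotyping, each at Month 12 and Month 24.
- **FISH:** Protocol 5.2.5.1 requires marrow FISH results before conditioning. Table 3 does not list FISH, and Table 4 schedules none. Protocol 6.2.29 places it in clinical work-up.
- **Stored samples:** Protocol 6.2.18 says that, if available, "bone marrow and blood samples collected per SOE may be used for retrospective genetic testing".

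**The concern.** The table is the planned group-level summary of acquired genetic change after busulfan conditioning and vector integration. For that purpose the useful count is subjects with a malignancy-associated abnormality that they did not have before. The planned table differs in three ways.

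1. It counts any abnormality, so a finding with no link to malignancy weighs the same as one with such a link.
2. It compares subject totals between periods and never compares a subject's later findings with that subject's own earlier ones.
3. The later period has more scheduled NGS and karyotype specimens, so having at least one positive can become more likely without any biological change.

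The table could therefore fail to show a true new finding, or show a rise that partly reflects extra sampling.

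**Working it through.** The SAP states no figure for this table, so there is none to reproduce. The check sets the texts side by side and then sizes the sampling effect under stated assumptions.

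**Step 1: endpoint against table.** The endpoint restricts to malignancy-associated findings; the table does not. The endpoint is followed over time; the table has two periods and their union. SAP Table 12 already defines Month 12 and Month 24 windows for karyotyping and NGS, but 4.6.10 does not report by them.

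**Step 2: what one row shows.** Take a single test and sample-type row.

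| Subject | <Day 1 | ≥Day 1 | Overall |
|---|---|---|---|
| A: unrelated finding before, persists | 1 | 1 | 1 |
| B: as A, plus a new malignancy-associated finding | 1 | 1 | 1 |
| C: nothing before, new malignancy-associated finding | 0 | 1 | 1 |
| D: nothing detected before, unrelated finding after | 0 | 1 | 1 |

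Overall minus <Day 1 is C + D. It misses B and does not separate C from D. Subjects like A and B are possible by design. Protocol 6.2.11 withdraws subjects whose marrow abnormality before conditioning is judged to raise MDS/AML risk, but lets subjects with other chromosomal abnormalities proceed after approval and consent.

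**Step 3: scheduled specimens (Protocol Tables 3 and 4).**

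| Row | Before | After |
|---|---|---|
| Blood NGS | 1 | 2 |
| Marrow NGS | 0 | 2 |
| Marrow karyotype | 1 | 2 |
| NGS, blood and marrow pooled | 1 | 4 |
| Marrow FISH | required (5.2.5.1) | none scheduled |

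The follow-up counts are scheduled maxima, because post-infusion marrow may be omitted as an exception (Protocol 6.2.17). In the other direction, 4.6.10 does not limit the later column to scheduled samples, so work-up specimens could add to it.

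**Step 4: size of the sampling effect.** The documents give neither a positive rate nor a detection probability, so both are assumptions. N = 36 is the number infused in Group C (SAP Table 1). Neither model contains a treatment effect.

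*Independent positives.* P(at least one in k specimens) = 1 − (1 − p)^k. With p = 0.10:

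- k = 1: 10%, or 3.6 of 36.
- k = 2 (blood NGS after): 1 − 0.9² = 19%, or 6.8 of 36.
- k = 4 (pooled NGS after): 1 − 0.9⁴ = 34.4%, or 12.4 of 36.

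With p = 0.02, the pooled comparison is 2.0% against 7.8%.

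*Stable pre-existing findings, imperfect detection.* Expected positives = 36 × π × [1 − (1 − s)^k], with prevalence π = 0.20 and detection s per specimen.

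| s | Before (k = 1) | Blood NGS after (k = 2) | Pooled NGS after (k = 4) |
|---|---|---|---|
| 0.5 | 3.6 | 5.4 | 6.75 |
| 0.7 | 5.0 | 6.6 | 7.1 |
| 0.9 | 6.5 | 7.1 | 7.2 |
| 1.0 | 7.2 | 7.2 | 7.2 |

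The effect falls to zero when findings are stable and always detected. Steps 1 and 2 do not depend on these assumptions.

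**The case against.** The strongest reply is that the table tells the reader more than the three counts suggest.

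- **The sample-type split.** A reader might infer that four NGS specimens after infusion are set against one before throughout. That holds only where blood and marrow are pooled. Within rows the counts are 2 against 1 for blood NGS and for karyotype. For marrow NGS they are 2 against 0, which shows openly as an empty baseline. This stands.
- **FISH runs the other way.** It is required before conditioning and not scheduled afterwards, so the imbalance in that row is reversed and partly offsets in the all-tests row. This stands.
- **Emergent findings are not invisible.** A reader might infer that the table cannot show treatment-emergent mutations at all. The documents do not support that. Overall minus <Day 1 gives subjects first positive after infusion, and with about 50 treated subjects the dated listings allow tracing case by case. This stands, except for subjects like B and for the mixing of C with D. The masking also needs both findings in the same row: an earlier karyotype finding does not hide a later NGS finding in the NGS row.
- **Laboratories may report only relevant findings.** Protocol 6.2.18 says that the testing looks particularly for MDS- and AML-associated abnormalities. The documents do not show the panel or the reporting rules, so how often unrelated findings would enter the count is unknown. The SAP nevertheless sets no restriction.
- **Nothing formal depends on the table.** No test or enrollment-suspension criterion uses it. Subject-level monitoring runs under Protocol 6.2.28 and 6.2.29, and the SAP summarizes malignancies and oligoclonality separately. This limits the harm but does not make the count match its endpoint.

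**Conclusion.** The point holds for the summary table. As written, SAP 4.6.10 yields a count wider than the endpoint in Protocol 2.2.3 and SAP 1.2.6.6. It has no within-subject category for new findings, and it misses a new malignancy-associated abnormality in a subject already positive in the same test and sample-type row. This conclusion rests on the text alone.

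The sampling imbalance is a secondary problem of undetermined size. It ranges from nothing, with stable and always-detected findings, to 19% against 10% for blood NGS or 34% against 10% for pooled NGS. Those upper figures assume an independent 10% positive rate per specimen. Independence is an extreme case for blood and marrow taken from one person at one visit. The documents therefore do not support predicting a false rise of any particular size.

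**What to change.** Revise SAP 4.6.10 as follows.

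1. Make the main row the number of subjects with at least one new malignancy-associated abnormality. Define new as not detected in that subject's pre-conditioning sample by the same test and sample type.
2. Report it at Month 12 and Month 24, using the existing Table 12 windows for karyotyping and NGS.
3. Show pre-existing or persistent findings, and findings not associated with malignancy, in separate rows.
4. Label post-infusion marrow NGS findings as having no baseline comparator, unless stored pre-conditioning marrow has been tested. Protocol 6.2.18 allows such testing where samples are available; it should remain optional.
5. Footnote that FISH has no scheduled follow-up.

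The cost is a one-time medical classification of abnormalities already listed, revised SAP wording and reprogramming of one table. No new visit or procedure is needed. Assays on stored marrow are an extra cost only if that comparator is wanted.
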